1. INTRODUCTION/BACKGROUND

Asthma affects more than 235 million people worldwide, including approximately 8.6% of U.S children (6.3 million children).^{1,2} Asthma treatment is a substantial burden to the healthcare system and is responsible for more than 10 million medical office visits (close to 6% of all US medical office visits) and 1.8 million ED visits each year.³ Regular use of controller medication is essential to prevent symptoms and relieve asthma exacerbations and thus decrease healthcare utilization and expenditure.⁴

Non-adherence to asthma medication is a common problem in patients with asthma, and young people are known to have particularly low medication adherence.^{5,6} Non-adherence leads to overuse of reliever medication and more frequent severe asthma exacerbations including ED visits and hospital admissions.^{4,7} Self-report consistently overestimates medication adherence making accurate assessment and intervention difficult for clinicians.⁵ However, two recent reviews found mean controller adherence ranging from 20% to 34% and 38% to 71% as measured by medication possession ratio (MPR) and electronic monitoring respectively.^{8,9} Thus, even the commonly cited statistic of 50% average medication adherence may underestimate the true scope of the problem.¹⁰⁻¹² Non-adherence is multifactorial, with contributing factors including lack of patient knowledge about asthma, poor understanding of the benefits of medication, forgetfulness, and negative attitude toward asthma.⁹

Telemanagement of chronic diseases is increasingly being employed to improve medication adherence and health outcomes, and has been shown to be cost-effective.¹³ A recently developed process model for optimal asthma care demonstrates the need for improved understanding of patient medication use behavior and how adherence interventions can impact clinical outcomes.¹⁴ A number of studies have improved medication adherence through incorporation of electronic reminders such as text messages across the spectrum of chronic diseases.¹⁵ Recently a number of studies have looked specifically at the use of such messages along with medication-use tracking in asthma have been able to show mean improvement in adherence from 10-52 percentage points.¹⁶⁻²³ While promising, these interventions have focused on the use of audiovisual reminder systems^{16, 21-23} that rely on having access to the inhaler itself or are simply based on SMS messages.^{17,18} Such interventions are limited in their ability to engage participants for improved disease self-management and self-monitoring compared to more comprehensive approaches, known to be key for sustained asthma telemanagement and mHealth approaches.¹³

Importantly, mobile applications allow for better sustained patient engagement and have been successfully implemented in other disease spaces to improve medication adherence and outcomes.¹³ Mobile applications offer the opportunity to be scaled to the U.S. population-at-large and can be sustained due to the front-end cost of development and low staff resources required for maintenance once the product is built. Additionally, the ability to relay adherence data directly to clinicians either via a patient portal or into the EMR provides opportunity to direct care coordination efforts and resources towards those participants who are most in need, and provides information that can be used for point-of-care treatment decision making.

2. STUDY TITLE

A prospective, randomized, controlled study to assess medication adherence in children with asthma managed on BreatheSmart and feedback.

3. JUSTIFICATION

Non-adherence to controller medication is a common problem in children with Asthma, resulting in overuse of reliever medication, increased asthma symptoms, more frequent Asthma attacks, and increased emergency room visits and hospital admissions.⁴ Additionally, current absence of a gold standard to measure adherence forces clinicians and researchers to rely on patient-self report, which is notoriously inaccurate, to support clinical decision making. Many young patients suffer from both intentional and non-intentional non-adherence, thus an appropriate intervention must address both types. Current studies using electronic monitoring devices (EMDs) primarily focus on non-intentional non-adherence through reminder systems and thus are limited in their ability to engage patients for long-term behavior change.

This trial addresses an important knowledge gap by evaluating whether EMDs with a combination of reminder system and patient education can prove to be effective in increasing adherence rates and can be used in clinical practice to achieve better asthma control and outcomes through improved patient and clinician engagement.

4. OBJECTIVES

The objectives of this study are to determine if the addition of the BreatheSmart platform improves medication adherence and health outcomes in children with persistent asthma who are managed with inhaled corticosteroids.

5. BREATHESMART

5.1.BreatheSmart

A mobile application designed for use with iOS and Android operating systems. Using Bluetooth to connect, this mobile application syncs with HeroTracker to facilitate the collection of medication adherence data.

5.2. HeroTracker

A wireless Bluetooth-enabled inhaler sensor that tracks medication dosage and adherence. Designed for both controller and rescue medications in diskus and MDI formats.

5.3. CoheroConnect

A HIPAA compliant cloud-based application allowing data to be aggregated and readily available as actionable information for clinicians and caregivers managing children on BreatheSmart.

6. STUDY DESIGN

This is a prospective, randomized, controlled study of children with persistent asthma who are managed on daily inhaled corticosteroids (ICS). 75 children will be randomized **2:1** into one of two arms:

- 50 children will be randomized to BreatheSmart, comprised of:
 - BreatheSmart mobile application that tracks medication usage and sends real time reminders
 - HeroTracker sensor that counts dosage and monitors real-time medication adherence
 - CoheroConnect provider portal that allows the Investigator to monitor real-time adherence and to provide targeted outreach to children with low adherence (intervention arm)
- 25 children will be randomized to “standard of care” (control arm). These patients are reminded to adhere to the prescribed standard of care therapy provided by their clinician during their clinical encounters and when the family calls to report an illness.

6.1.Endpoints

6.1.1 Primary:

The study's primary objective is to estimate the relative improvement in medication adherence among children using BreatheSmart with feedback compared to control at 6 months.

6.1.2 Secondary:

Important secondary objectives include the extent to which BreatheSmart system improves the following when compared to control from baseline to 6-months:

- asthma control as measured by the Childhood Asthma Control Test (ACT)
- lung function as measured by FEV1 and FEV1/FVC ratio compared to standard of care
- the correlation between changes in medication adherence and changes in FEV1 and FEV1/FVC ratio.
- the overall number of provider visits for asthma related adverse events (number of exacerbations leading to acute Provider intervention, ER visits, hospitalizations, or requiring oral systemic corticosteroid therapy)
- number of missed school days

7. STUDY POPULATION

This study will enroll children who have been diagnosed with persistent asthma for at least 6 months' duration and who are showing evidence of poorly controlled disease. 75 children will be recruited from CT Children's Medical Center Pulmonary Clinic and East and West Primary Care.

7.1.Inclusion and Exclusion Criteria

Inclusion and Exclusion Criteria

Inclusion criteria:

- Age 8 to 17
- Diagnosis of persistent asthma
- Prescribed an inhaled corticosteroid (ICS) for at least one month prior to enrollment
- Use of a pressurized metered dose inhaler (pMDI) compatible with the Cohero mHealth Herotracker (See Appendix)
- Parent/child possess a compatible smartphone (iOS 8.0 or higher)
- English or Spanish speaking

Exclusion criteria:

- Presence of another chronic lung disease or condition such as cystic fibrosis, interstitial lung disease, chronic lung disease of prematurity, recurrent aspiration, or presence of tracheostomy
- Presence of other chronic medical condition such as congenital heart disease or immunodeficiency
- Presence of other comorbidities that, in the opinion of the investigator, will interfere with collection of study procedures, or limits life expectancy to < 1 year
- Currently pregnant or planning to become pregnant during the trial period

7.2. Sample Size Estimates

There is no pilot data available to inform a sample size analysis. In addition, our sample size is limited by our supply of HeroTracker devices (50). As this is an exploratory study, we hope our findings will inform future sample size analyses for studies of similar focus with a larger cohort.

7.3. Recruitment

Due to the shortage of space and high patient volume at the CCMC pulmonary office, based on the scheduled patients for the day, research personnel will identify potentially eligible patients based on information will be gathered from the “Pulmonary Snapshot” feature in EPIC. These data include patient age, asthma diagnosis and prescribed medicines. Research personnel will also be identifying potentially eligible patients at the East and West Primary care through the “Primary Care Sanpshot” features in EPIC. Potential participants will only be approached if he/she meets the following inclusion criteria: age between 8-17 years, documented diagnosis of persistent asthma and/or prescription of an inhaled corticosteroid. Once this is confirmed, the research personnel will approach the patient to administer the screening questionnaire to confirm that the child meets all the inclusion and exclusion criteria. Children could also be referred to this study by their healthcare provider if he/she feels that the patient qualifies for entry into the study based upon the Inclusion/Exclusion Criteria. If eligible, the parent will be asked to participate in the study and presented with the informed consent document which will include the parent’s consent to utilize the relevant screening and baseline data for the purposes of this study.

7.4. Informed Consent

The primary investigator (or designee) will discuss the study in detail with the child and parent and describe the potential risks and benefits. If the parent agrees for their child to participate, a legally effective informed consent will be obtained. The consent process will be documented in the study chart and the parent will receive a copy of the fully executed informed consent form for their records. All children participating in this study will complete assent.

7.5. Participant Numbering

To maintain confidentiality, the participant's name will not be recorded on any study documents other than the informed consent form. All participants that provide informed consent will be assigned a unique alphanumeric code that will identify them throughout the course of the study.

8. STUDY PROCEDURES

All participants will be seen at screening/baseline, 90 and 180 days' post randomization where the following assessments will be performed.

8.1. Screening Assessments

The study staff will interview the parent and child and document the following:

- Type of mobile device and version number of the operating system in use
- Email address
- Age/gender/ethnicity
- Parent Income level/education level/medical insurance type
- Date of asthma diagnosis
- Other comorbidities
- Use of inhaled corticosteroids and other inhaled therapies for asthma
- Use and timing of oral systemic corticosteroids
- Use of other concomitant medications
- Medication refill information (obtained through pharmacy records)
- ACT

8.2. Randomization

If the child is eligible and they wish to participate they will be randomized in a 2:1 allocation to BreatheSmart or to standard of care. As we have a limited supply of HeroTracker devices and the CoHero platform does not provide a feasible way to execute any degree of blinding, this will be conducted as an open trial where both groups (control and intervention groups) will be treated as equally as possible. Randomization will be stratified by age at the time of enrollment (8-13 years, 14-17 years) and blocked in randomly permuted sequences of 4.

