8.4. Follow-up

All participants in both groups will be seen at 90 and 180 days' post randomization (+/-20 days) correlating with routine pulmonary clinic follow up and East and West Primary Care Follow up where the following assessments will be recorded:

- Medication changes/refills (obtained through pharmacy record)

- FEV1, FEV1/FVC, FEF25-75 and FeNO per clinical standard of care (only assessed in the Pulmonary clinic)
- Child Asthma control test (ACT) questionnaire
- Serious Adverse Events will be recorded at each visit
- Missed school days
- PedsQL asthma module (patient and parent report)
- Test of Adherence to Inhalers
- Exacerbation of asthma episodes (obtained through self-report and chart review) requiring:
 - Doctor visits outside of standard of care
 - ER visits
 - Hospitalizations

In addition, active participants (test group) will be continuously monitored via the CoheroConnect dashboard which allows the Investigator to monitor the child's medication adherence in real time. If a period of participant inactivity of 3 days is registered in the system, the Investigator (or designee) will be notified and he/she will be prompted to contact the participant to remind them to take their medication as prescribed. The Investigator or designee will review patient specific data (% adherence since last visit and graph of adherence patterns over time since enrollment) through the CoheroConnect dashboard within two days before a follow up visit. At the follow-up visit, these data will be reviewed with the patient and parent/caregiver. The adherence rate and barriers identified will be discussed and, if necessary, personalized strategies for improvement will be devised. These data will also be shared with the clinician during these follow up visits. Medication adherence data for control participants will be obtained by measure of pharmacy record refill information and self-report (Test of Adherence to Inhalers) throughout the duration of the study.

We understand that the self-report of missed school days due to asthma may be unreliable and subject to recall bias, however, this is the method we currently use clinically to assess this measure.

If a participant is unable to complete the follow-up visit at their routine pulmonary appointment, the coordinator will either mail, text a link, or email a link of the follow-up surveys to the participants. They will be reminded 3 times via text, email or phone to complete the follow-up questionnaires.

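### Nothing stops siblings from entering opposite arms, so a control child may receive part of the intervention through a shared caregiver; the likely size is small and the remedy is cheap

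*Combined protocol and SAP*

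**What the plan says.** Section 8.2 (Randomization) makes the child the unit of allocation: once eligible and willing, "they will be randomized in a 2:1 allocation to BreatheSmart or to standard of care". The only stratification factor is age at enrolment, in two bands. Allocation is "blocked in randomly permuted sequences of 4", and "this will be conducted as an open trial". Section 6 (Study Design) sets the arm sizes: "50 children will be randomized to BreatheSmart", and "25 children will be randomized to" standard of care.

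Section 7.1 admits ages 8 to 17, a range that can include two siblings. It has no household or sibling criterion, and neither does section 7.3 (Recruitment). The interview items in section 8.1 (Screening Assessments) do not include household membership.

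Two features involve the parent. The device requirement in section 7.1 reads "Parent/child possess a compatible smartphone (iOS 8.0 or higher", so the phone may be the parent's or the child's; section 6 says the app on it sends reminders. In section 8.4 (Follow-up), the active child's adherence record is gone through with the patient and the parent or caregiver, and then: "The adherence rate and barriers identified will be discussed and, if necessary, personalized strategies for improvement will be devised".

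Section 10.4 bases the analyses on intention to treat. Section 10.5 compares mean change in adherence between groups with a t-test at the 0.05 level.

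**The concern.** Part of the intervention reaches the parent: the discussion of adherence, barriers and strategies at follow-up and, where the parent's phone is used, possibly the reminders. If the same parent also looks after a control child's inhaler, what is learned for one child can be applied to the other. The control child's adherence may then rise for a reason that the comparison is meant to exclude. Intention to treat correctly keeps that child in the control arm, so any dilution stays in the primary estimate and in the clinical outcomes.

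The smaller arm carries this effect: each exposed control is 1/25 = 4% of it. Without a household variable, the plan offers no way to identify exposed controls for a sensitivity analysis. The email address collected at screening might reveal some pairs, but the plan does not use it for that. Section 10.4 says the results may inform the sample size and expected efficacy of a larger study, so a diluted estimate could be carried forward.

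**Working it through.** **Inputs from the documents.** 2:1 allocation of individual children, age-only stratification and blocks of 4 (section 8.2); 50 active and 25 control (section 6); a t-test at the 0.05 level (section 10.5). The plan has no power calculation and no sibling count, so it has no figure of its own to reproduce.

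**Assumed inputs.** Number of sibling pairs m = 0, 2, 5 or 8; spill-over to an exposed control c = 50% or 100% of the intervention's benefit; within-pair correlation ρ of 0.5 or 0.8 for the t-test check.

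**1. Chance that a pair is split between arms.**
- Independent 2:1 allocation: 2 × (2/3) × (1/3) = 4/9 = 44%. This is the natural figure for siblings in different age strata, who are allocated from separate lists.
- Both siblings in the same block of 4: a block cannot hold an exact 2:1 split (4 × 2/3 = 2.67) and its composition is not stated. With 3 active and 1 control, 3 of the 6 possible pairs of places are split = 50%. With 2 and 2, 4 of 6 = 67%.

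**2. Exposed controls and dilution at 44%.** Exposed = m × 4/9. Share of controls = exposed / 25. Effect lost = c × share.

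| Pairs m | Exposed controls | Share of 25 | Effect lost, c = 50% | Effect lost, c = 100% |
|---|---|---|---|---|
| 0 | 0 | 0% | 0% | 0% |
| 2 | 0.9 | 4% | 2% | 4% |
| 5 | 2.2 | 9% | 4% | 9% |
| 8 | 3.6 | 14% | 7% | 14% |

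If all five pairs fell within shared blocks, the exposed number would be 5 × 0.50 to 5 × 0.67 = 2.5 to 3.3 controls, or 10% to 13%. That is an extreme case, because it needs every pair to share both a stratum and a block.

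**3. Scale against sampling error.** In standard-deviation units the standard error of the difference is √(1/25 + 1/50) = 0.245. The difference detectable with 80% power (two-sided 0.05, normal approximation) is (1.96 + 0.84) × 0.245 = 0.69. A 9% loss from 0.69 is 0.06, about a quarter of one standard error.

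**4. Does sibling correlation damage the t-test?** With independent children the variance of the difference is 1/50 + 1/25 = 0.06. A both-active pair adds 2ρ/50², a both-control pair adds 2ρ/25², and a split pair subtracts 2ρ/(50 × 25). These occur with probabilities 4/9, 1/9 and 4/9, so the expected change per pair is 2ρ × [(4/9)/2500 + (1/9)/625 − (4/9)/1250] = 2ρ × [0.000178 + 0.000178 − 0.000356] = 0.

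In 40,000 simulated trials per setting, with unstratified 50:25 assignment, type I error was 5.1% for 5 pairs at ρ = 0.5 and 5.1% for 8 pairs at ρ = 0.8.

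For a single realised allocation with 5 pairs at ρ = 0.5, the extremes are:
- all pairs split: variance 0.06 − 5/1250 = 0.056, type I error about 4.3%;
- all pairs both control: variance 0.06 + 5/625 = 0.068, type I error about 6.6%.

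**The case against.** The strongest objection is that the problem may not arise. Both siblings would have to be 8 to 17, have persistent asthma, have been prescribed an inhaled corticosteroid for at least a month, use a compatible inhaler, be identified or referred, and consent. Among 75 children the number of such pairs could be zero. The study is also exploratory, with its size set by device supply (section 7.2), so no stated power is undermined. Both points stand, and they make this a minor matter.

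Second, full spill-over is hard to defend. A control sibling has no sensor, no app and no missed-dose alert, the feedback is specific to the active child, and an older child may use their own phone. This also stands: the 100% column is an upper bound.

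A reader might infer two stronger claims. One is that the parent receives the prompt triggered by three days of inactivity. Section 8.4 directs that contact to the participant and does not name the parent; only the parent's part in the follow-up review is explicit. The other is that correlated siblings invalidate the t-test or its confidence interval. Individual allocation makes the covariance terms cancel on average, and split pairs, the case at issue here, make the test slightly conservative.

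What the objection does not answer is that the plan permits a split household, involves the parent in delivering the intervention, and does not record which households are affected.

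**Conclusion.** The point holds as a minor design improvement, limited to contamination. As written, the plan can place an active and a control child under one caregiver, and this would bias the adherence difference toward no effect if the intervention helps and some of the help carries over. Over 0 to 8 assumed pairs at the 44% split rate, the loss is between 0% and 14% of the effect with full spill-over, and half that with 50% spill-over. Both the pair count and the spill-over are assumptions, and the true loss may be close to zero. Sibling correlation is not a reason for the change, since average type I error stays at about 5%.

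**What to change.** Add to the exclusion criteria in section 7.1: *another child in the household is already enrolled*. Add one question to the section 8.1 screening interview to establish this. State a fixed rule for which child enters when more than one is eligible, for example the first with a scheduled visit, so that the choice is not left to staff or family.

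The cost is one criterion, one question and a few otherwise eligible children. Section 8.7 suggests that recruitment can absorb this: about 5 to 10 age-eligible asthma patients per clinic day on two days a week is 10 to 20 a week, against 4 to 5 planned enrolments, although not all of them will meet every criterion.

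If the sponsor prefers not to turn siblings away, households could be allocated as a unit, with clustering then handled in the analysis. Recording household membership for a sensitivity analysis is a weaker alternative: it would show the exposure but not prevent it.

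### A single stated block size of 4 in an open trial, with no concealment described, could let recruiting staff foresee some allocations

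*Combined protocol and SAP*

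**What the plan says.** Under Section 8.2, children are "randomized in a 2:1 allocation to BreatheSmart or to standard of care". The same section continues: "Randomization will be stratified by age at the time of enrollment (8-13 years, 14-17 years) and blocked in randomly permuted sequences of 4". It gives no other block size and does not say how many of the four places go to each arm. On blinding it says "this will be conducted as an open trial where both groups (control and intervention groups) will be treated as equally as possible".

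The people involved are described in four places:

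- **Section 7.3:** once the basic criteria are met, "the research personnel will approach the patient to administer the screening questionnaire to confirm that the child meets all the inclusion and exclusion criteria". Providers may also refer children they judge suitable.
- **Section 7.4:** the investigator or a designee takes consent.
- **Section 8.1:** screening, listed before randomization, records pharmacy refill information and the ACT.
- **Section 8.4:** the investigator or a designee monitors active-arm children on the dashboard and contacts them after three days of inactivity.

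Section 6 states the intended split: "50 children will be randomized to BreatheSmart", and 25 to standard of care. Section 7.2 says the sample size is limited by a supply of 50 HeroTrackers. Section 8.7 varies the time and day of recruitment in order to limit selection bias.

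No section says who generates or holds the sequence, how an assignment is released, or that the block size is kept from recruiting staff.

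**The concern.** In an open trial, past allocations are visible to whoever runs it. Someone who also knows the block length and composition can work out when one arm's places in the current block are used up, and then knows every remaining assignment in that block. Keeping the list locked away does not prevent this, because the knowledge comes from counting.

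Here the block length is printed in the protocol that staff work from. Enrolment is expected at 4-5 children a week, in only two age strata. The investigator or designee role both takes consent and follows active-arm children. Staff may have seen a child's refill history before the assignment is made. A family could therefore be approached, delayed or passed over in the light of what the next assignment will be.

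The primary analysis in Section 10.5 is a t-test on change in adherence, with no adjustment for baseline covariates described. Intention-to-treat analysis cannot undo selection that happens before randomization. Varying recruitment times, as in Section 8.7, does not close this route.

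**Working it through.** **Inputs.** Block size 4, two age strata, ratio 2:1 and open design (Section 8.2); 75 children, 50 and 25 (Section 6); 50 devices (Section 7.2). The documents give no block composition, so it is taken as a range. A is BreatheSmart and C is control. An assignment counts as certain when the earlier assignments in its block leave only one possibility.

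**The plan's own split.** The ratio gives 75 × 2/3 = 50 and 75 × 1/3 = 25, as stated. Blocks of 4 do not, because 4 × 2/3 = 2.67 is not a whole number. All blocks 3:1 would give 75 × 3/4 = 56.25 active; all blocks 2:2 would give 37.5. Neither is 50:25.

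**All blocks 3:1.** The control child is equally likely in positions 1 to 4, which leaves 3, 2, 1 and 1 later assignments certain. (3 + 2 + 1 + 1)/(4 × 4) = 7/16 = 43.75%.

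**All blocks 2:2.** There are six orders. AACC and CCAA leave two certain each, and the other four leave one each. (2 + 2 + 4)/(6 × 4) = 8/24 = 33.3%.

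**Composition varied at random, two-thirds 3:1 and one-third 2:2.** Mean active per block is 2/3 × 3 + 1/3 × 2 = 2.67, which averages 2:1.

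- AAAC has probability 2/3 × 1/4 = 1/6 and leaves one certain.
- Each 2:2 order has probability 1/3 × 1/6 = 1/18. CCAA leaves two certain; ACCA and CACA leave one each.
- Every other order leaves none.
- Expected number per block: 1/6 + (2 + 1 + 1)/18 = 7/18 = 0.389. Share: 0.389/4 = 9.7%.

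**Fixed block of 3 (2:1).** (2 + 1 + 1)/(3 × 3) = 4/9 = 44.4%.

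**Randomly varied sizes, all exactly 2:1.** These come from simulated lists of 75, with sizes equally likely and an observer who knows the possible sizes and the full history.

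| Scheme | Certain in advance | Of 75 |
|---|---|---|
| Fixed 4, all 3:1 | 44% | about 32 |
| Fixed 4, all 2:2 | 33% | about 24 |
| Fixed 4, mixed to average 2:1 | 9.7% | about 7 |
| Fixed 3 | 44% | about 33 |
| Sizes 3 and 6 | about 10% | about 8 |
| Sizes 3, 6 and 9 | about 4% | about 3 |

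The counts for the fixed 3:1, 2:2 and block-of-3 schemes come from simulating 75 children in two strata, where the last block in each may be incomplete. The other counts are the share × 75.

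**Device limit.** With sizes 3, 6 and 9, a stratum that stops after six actives in a block of 9 has 6 − 6 × 2/3 = 2 more than 2:1. Two strata give at most 50 + 4 = 54. In simulated lists the active arm passed 50 in about 12% to 27%. With sizes 3 and 6, stopping after three actives in a block of 6 in both strata gives 3 − 2 = 1 extra each, so 52, which is the most those sizes allow for 75 children.

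**The case against.** The strongest objection is to the size. A reader might infer that staff will know 44% of assignments. That figure needs every block to be 3:1 and the observer to know it. Such blocks would give about 56:19, not the stated 50:25, and would exceed the device supply. A mixed composition that does average 2:1 gives 9.7%, no worse than the remedy with sizes 3 and 6. This stands: the plan does not settle the figure, and only the range can be reported. The protocol does not describe the mixed scheme either.

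A reader might also infer that recruiters see every allocation. The documents do not say so. They name research personnel for approach and screening, and the investigator or a designee for consent and follow-up; overlap is a reasonable inference and no more. Because randomization is not stratified by site, an observer would need running counts by age stratum across the pulmonary and primary care clinics. The percentages are therefore ceilings for a perfect observer.

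A third inference, that the bias falls directly on the primary comparison, is not supported. The outcome is change from baseline, so steering a known good adherer into one arm raises that arm's baseline too, and the direction is unclear.

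Finally, Section 8.2 already randomizes only eligible, willing children, Section 11.4 requires prior consent, and the study calls itself exploratory. These points lower the stakes. They do not stop someone from anticipating the next assignment before deciding whom to approach.

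**Conclusion.** The concern holds as an avoidable opportunity for selection bias. One stated block size, an open design, overlapping roles and no described concealment together make some assignments foreseeable. The share certain to an observer who tracks every allocation lies between about 10% and 44%, depending on a block composition that the protocol leaves open. Nothing in the documents shows that selection occurred, or how far or in which direction it would move the change-from-baseline comparison.

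The result rests on two assumptions: that enrolling staff can learn past allocations, and that they know or can infer the composition. The same sentence of Section 8.2 must be revised anyway, because blocks of 4 cannot be exactly 2:1. If that is done with a fixed block of 3, predictability stays at 44%. The change should be made, but the point is not fatal to an exploratory trial.

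**What to change.** When the block size is reconciled with 2:1:

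- Generate the list within each age stratum with randomly varied block sizes that are multiples of 3.
- Record the sizes only in the list-holder's file, and remove them from the protocol that recruiters hold.
- State who generates and holds the list. Release each assignment only after consent, assent and eligibility are recorded, for example through Qualtrics, which the study already uses, or opaque sequential envelopes.
- Before enrolment, have the list-holder check the list against the 50 devices over the plausible splits between age strata. Using 3 and 6 only lowers the worst case from 54 to 52 but does not remove the need for the check; the alternative is to choose a list that stays within 50.

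The choice of sizes is a trade-off. Sizes 3, 6 and 9 give the lowest predictability; 3 and 6 give tighter control of the split, but no gain in certainty over a mixed-composition block of 4.

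The cost is a regenerated list and a short amendment to Section 8.2, which needs IRB approval under Section 11.6. No visits or assessments are added. The final split may miss 2:1 by a few children in total.
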